6.4.3. Posttreatment Week 24 (\pm 5 days)

The following procedures/assessments are to be completed for all subjects, 24 weeks after taking the last dose of study drug:

- Perform complete physical examination (refer to Section [6.7.3](#))
- Obtain weight
- Obtain vital signs (refer to Section [6.7.4](#))
- Conduct pregnancy prevention counseling
- Obtain blood samples for tests (approximately 25 mL of blood will be drawn total):
 - HCV RNA
 - Viral RNA Sequencing / Phenotyping Sample and/or HBV DNA Sample
- Obtain urine sample for:
 - Pregnancy test for females of childbearing potential only

6.5. Early Termination (ET)

For subjects who have completed an ET visit, the posttreatment Week 4, 12, and 24 follow-up visits will be scheduled after the last dose of the study drugs.

When medically feasible, the medical monitor must be consulted prior to subject discontinuation.

The following procedures/assessments are to be completed at an Early Termination visit:

- Perform complete physical examination (refer to Section [6.7.3](#))
- Obtain weight
- Obtain vital signs (refer to Section [6.7.4](#))
- Assessment of AEs and concomitant medications
- Conduct pregnancy prevention counseling
- Subject completes Health Related Quality of Life (HRQoL) surveys (refer to Section [6.7.6](#))
- Assess adherence with study drug dosing regimen including pill count. Collect any remaining study drug from the subject
- Obtain blood samples for tests (approximately 35 mL of blood will be drawn for required tests):
 - Hematology
 - Chemistry
 - Coagulation tests
 - HCV RNA
 - Viral RNA Sequencing / Phenotyping Sample and/or HBV DNA Sample
 - Single PK sample
 - Archive plasma sample (for subjects who have consented) (an additional 12 mL of blood will be drawn)
- Obtain urine sample for:
 - Pregnancy test for females of childbearing potential only

6.6. Unscheduled Visit

A subject should attend an unscheduled visit if requested by the sponsor or the investigator. The assessments are at the investigator's discretion as clinically indicated, but the investigator should, at a minimum, collect AE and concomitant medication information. At all unscheduled visits initiated for the purpose of confirming virologic failure, a sample for a viral RNA sequencing/phenotyping must be collected.

6.7. Procedures and Specifications

6.7.1. Clinical Laboratory Analytes

Hematology: Hematocrit, Hemoglobin (Hb), Platelet count, Red blood cell count (RBC), White blood cell count (WBC) with differential (absolute and percentage) including Lymphocytes, Monocytes, Neutrophils, Eosinophils, and Basophils and, Reticulocyte count and mean corpuscular volume (MCV).

Coagulation: INR, Prothrombin time (PT), Activated partial thromboplastin time (aPTT)

Chemistry: Alanine aminotransferase (ALT/SGPT), Aspartate aminotransferase (AST/SGOT), Albumin, Alkaline phosphatase, Creatine Kinase, Creatinine, Direct Bilirubin (at screening and reflexed from total bilirubin at other visits), Total Bilirubin, Glucose, Lipase, Potassium, Sodium, FibroTest® (at Screening only).

Urinalysis: Blood, Glucose, Leukocyte esterase, pH, Protein, Urobilinogen. Reflex to microscopic urinalysis if dipstick result is abnormal.

Virological Tests: Serologies for HCV and HBV. HBV DNA (reflex testing done when ALT > 2x Day 1 value in subjects who are HBsAb or HBcAb positive at Screening). Serology and/or antigen testing for HIV, including reflex testing as necessary. HCV RNA will be measured using the COBAS® AmpliPrep/COBAS® TaqMan® HCV Quantitative Test, version 2.0. HCV genotype and subtype will be determined using the Siemens VERSANT® HCV Genotype INNO-LiPA2.0 Assay. Gilead reserves the right to use alternate assays for HCV RNA and HCV genotype should the above assays become unavailable or are not definitive.

IL28B genotype will be determined by polymerase chain reaction (PCR) amplification of the SNP, rs12979860, with sequence specific forward and reverse primers and allele specific fluorescently labeled TaqMan® MGB probes. Gilead reserves the rights to use an alternate assay for IL28B determination should the above assay become unavailable.

Pregnancy Tests: Serum β-hCG or Urine β-hCG (if positive, requires immediate confirmation with Serum β-hCG).

Additional Tests: Hemoglobin A1c (HbA1c, screening only).

6.7.2. Medical History

Medical history, including details regarding illnesses and allergies, date(s) of onset, and whether condition(s) is currently ongoing, and medication history will be collected on all subjects during screening.

Obtain HCV treatment history in order to confirm eligibility of the subject as per Inclusion Criteria #7. Information related to HCV infection will also be collected.

6.7.3. Complete Physical Examination

A physical examination must include source documentation of general appearance, and the following body systems: Head, neck, and thyroid; eyes, ears, nose, throat, mouth, and tongue; chest (excluding breasts); respiratory; cardiovascular; lymph nodes; abdomen; skin, hair, nails; musculoskeletal; neurological.

6.7.4. Vital Signs

Assessment of vital signs will include measurement of resting blood pressure, pulse, respiratory rate, and temperature.

Blood pressure will be measured using the following standardized process:

- Subject should sit for \geq 5 minutes with feet flat on the floor and measurement arm supported so that the midpoint of the manometer cuff is at heart level;
- Use a mercury sphygmomanometer or automatic blood pressure device with an appropriately sized cuff with the bladder centered over the brachial artery;
- Measure and record the blood pressure to the nearest 2 mmHg mark on the manometer or to the nearest whole number on an automatic device.

6.7.5. 12-Lead ECG

Subjects will be required to rest in a supine position for \geq 5 minutes prior to making a recording. The investigator (or qualified designee) should review the ECG traces recorded in real time for clinically significant abnormalities.

6.7.6. Health Related Quality of Life (HRQoL)

Health Related Quality of Life surveys (HRQoL) included in this study are the SF-36, Chronic Liver Disease Questionnaire (CLDQ-HCV), Fatigue Index (FACIT-F), and Work Productivity and Activity Impairment Questionnaire: Hepatitis C, v2.0 (WPAI: Hepatitis C).

The Health Related Quality of Life surveys (HRQoL) will only be administered to subjects if available at Day 1, Week 12, Week 24 (if applicable), and Posttreatment Week 12. The subject should read the questionnaire by himself/herself and record the answers by himself/herself.

6.7.7. Viral RNA Sequencing / Phenotyping Sample

Plasma samples will be collected at Day 1 and each visit thereafter and may be archived for viral sequence analysis. At any unscheduled visit initiated for the purpose of confirming virologic breakthrough, a viral sequence analysis plasma sample must be collected.

Details regarding the collection, processing, and shipping of samples will be included in the lab manual.

6.7.8. Single Pharmacokinetic (PK) Sample

Single PK blood samples will be collected for all subjects at each on-treatment visit and archived for PK analysis of SOF, its metabolites, VEL, and RBV (if appropriate). Approximately 6 mL of whole blood will be collected for each sample (which is included in the total blood volume amounts in Sections 6.1, 6.2, 6.3, and 6.5). The exact time the study drugs were taken and whether or not the study drugs were taken with food on PK assessment days will be recorded in the source documents and eCRF.

Details regarding the collection, processing, and shipping of samples will be included in the lab manual.

6.7.9. Intensive Pharmacokinetic (PK) Substudy

PPD

6.7.10. Pregnancy Testing

All females of childbearing potential will have a serum pregnancy test at Screening. Urine pregnancy testing will occur at Day 1 and every 4 weeks during the dosing period.

Females of childbearing potential will have additional urine pregnancy testing every 4 weeks for a minimum of 6 months following last dose of RBV. If required by local regulations, additional pregnancy tests beyond 6 months may be added. In the event of a positive urine pregnancy result, subjects will be instructed to return to the clinic as soon as possible for a serum pregnancy test. Pregnancy test kits will be dispensed to female subjects of childbearing potential after the posttreatment Week 4 visit. The subject will be contacted by telephone monthly to confirm that urine pregnancy testing has been performed posttreatment and to record the outcome. Alternatively, if required by local regulations or preferred by the investigator or subject, the subject may return to the clinic for urine pregnancy tests.

6.7.11. IL28B Testing

A blood sample will be obtained at screening for specific genetic analysis of the rs12979860 (IL28B) genetic variant.

6.7.12. Archive Plasma Sample

For subjects who provide consent, an archive plasma sample (non-genetic) will be collected at Day 1, Week 12, Week 24 (if applicable) and Early Termination (if applicable) Visits.

Approximately 12 mL of whole blood will be collected for each sample. The specimens collected will be used to increase our knowledge and understanding of the biology pathogenesis, progression and/or treatment outcomes, including efficacy, AEs, and the processes of drug absorption and disposition. These specimens may be used for retesting of the amount of HCV in the blood, clinical laboratory testing to provide additional clinical data and to develop non-genetic biomarker or diagnostic assays and establish the performance characteristics of these assays.

Details regarding the collection, processing, and shipping of samples will be included in the lab manual. At the conclusion of this study, these samples may be retained in storage by Gilead Sciences, Inc. for a period up to 15 years after the end of the study. These samples will be destroyed by internationally accepted means (eg, incineration).

6.7.13. Genomic Testing

This study also includes the optional collection of a whole blood sample for human genomic testing. This sample may only be collected following approval of site IRB or Ethical Committees. In addition to the study-specific informed consent to be signed by each subject participating in the study, a separate, specific signature will be required to document a subject's agreement to provide this additional sample for optional genomic research. Provision of the genomic sample is optional and is not required in order for a subject to participate in the study.

From subjects who agree to participate and provide their additional specific consent, one blood sample of approximately 6 mL of whole blood will be collected. This sample should be collected at the Day 1 visit, but may be collected at any time during the study or at a separate post study visit, if necessary. **PPD**

The subject's identity will be protected, and the subject's name will not be attached to the sample. The sample may be stored for up to 15 years before being destroyed. The sample will be destroyed by internationally accepted means (eg, incineration).

Details regarding the collection, processing, and shipping of samples will be included in the lab manual.

6.7.14. Creatinine Clearance

Creatinine clearance is calculated by the Cockcroft-Gault equation {Cockcroft et al 1976} using actual body weight (ABW).

$$\text{Male: } \text{Cr}_{\text{cl}} \text{ (mL/min)} = \frac{[140 - \text{age (years)}] \times \text{ABW(kg)}}{72 \times \text{S}_{\text{cr}}}$$

$$\text{Female: } \text{Cr}_{\text{cl}} \text{ (mL/min)} = \frac{[140 - \text{age (years)}] \times \text{ABW(kg)} \times 0.85}{72 \times \text{S}_{\text{cr}}}$$

S_{cr} = serum creatinine (mg/dL)

6.8. End of Study

Subjects are considered to have completed the study after the posttreatment Week 24 visit, regardless of treatment duration or early termination of study drugs.

6.9. Poststudy Care

No poststudy ongoing care will be provided.

7. ADVERSE EVENTS AND TOXICITY MANAGEMENT

7.1. Definitions of Adverse Events, Adverse Reactions, and Serious Adverse Events

7.1.1. Adverse Events

An adverse event (AE) is any untoward medical occurrence in a clinical study subject administered a medicinal product, which does not necessarily have a causal relationship with the treatment. An AE can therefore be any unfavorable and/or unintended sign, symptom, or disease temporally associated with the use of a medicinal product, whether or not considered related to the medicinal product. AEs may also include pre- or posttreatment complications that occur as a result of protocol specified procedures, overdose, drug abuse/misuse reports, or occupational exposure. Preexisting events that increase in severity or change in nature during or as a consequence of participation in the clinical study will also be considered AEs.

An AE does not include the following:

- Medical or surgical procedures such as surgery, endoscopy, tooth extraction, and transfusion. The condition that led to the procedure may be an adverse event and must be reported.
- Pre-existing diseases, conditions, or laboratory abnormalities present or detected before the screening visit that do not worsen
- Situations where an untoward medical occurrence has not occurred (eg, hospitalization for elective surgery, social and/or convenience admissions)
- Overdose without clinical sequelae (see Section [7.6.1](#))
- Any medical condition or clinically significant laboratory abnormality with an onset date before the consent form is signed and not related to a protocol-associated procedure is not an AE. It is considered to be pre-existing and should be documented on the medical history eCRF.

7.1.2. Serious Adverse Events

A **serious adverse event** (SAE) is defined as an event that, at any dose, results in the following:

- Death
- Life-threatening (Note: The term “life-threatening” in the definition of “serious” refers to an event in which the subject was at risk of death at the time of the event; it does not refer to an event that hypothetically might have caused death if it were more severe.)
- In-patient hospitalization or prolongation of existing hospitalization
- Persistent or significant disability/incapacity

- A congenital anomaly/birth defect
- A medically important event or reaction: such events may not be immediately life-threatening or result in death or hospitalization but may jeopardize the subject or may require intervention to prevent one of the other outcomes constituting SAEs. Medical and scientific judgment must be exercised to determine whether such an event is a reportable under expedited reporting rules. Examples of medically important events include intensive treatment in an emergency room or at home for allergic bronchospasm; blood dyscrasias or convulsions that do not result in hospitalization; and development of drug dependency or drug abuse. For the avoidance of doubt, infections resulting from contaminated medicinal product will be considered a medically important event and subject to expedited reporting requirements.

7.1.3. Clinical Laboratory Abnormalities and Other Abnormal Assessments as Adverse Events or Serious Adverse Events

Laboratory abnormalities without clinical significance are not recorded as AEs or SAEs. However, laboratory abnormalities (eg, clinical chemistry, hematology, and urinalysis) that require medical or surgical intervention or lead to study drugs interruption, modification, or discontinuation must be recorded as an AE, as well as an SAE, if applicable. In addition, laboratory or other abnormal assessments (eg, electrocardiogram, x-rays, vital signs) that are associated with signs and/or symptoms must be recorded as an AE or SAE if they meet the definition of an AE or SAE as described in Sections 7.1.1 and 7.1.2. If the laboratory abnormality is part of a syndrome, record the syndrome or diagnosis (eg, anemia), not the laboratory result (ie, decreased hemoglobin).

7.2. Assessment of Adverse Events and Serious Adverse Events

The investigator or qualified subinvestigator is responsible for assessing AEs and SAEs for causality and severity, and for final review and confirmation of accuracy of event information and assessments.

7.2.1. Assessment of Causality for Study Drugs and Procedures

The investigator or qualified subinvestigator is responsible for assessing the relationship to study drugs using clinical judgment and the following considerations:

- **No:** Evidence exists that the adverse event has an etiology other than the study drugs. For SAEs, an alternative causality must be provided (eg, pre-existing condition, underlying disease, intercurrent illness, or concomitant medication).
- **Yes:** There is reasonable possibility that the event may have been caused by the study drugs.

It should be emphasized that ineffective treatment should not be considered as causally related in the context of adverse event reporting.

The relationship to study procedures (eg, invasive procedures such as venipuncture or biopsy) should be assessed using the following considerations:

- **No:** Evidence exists that the adverse event has an etiology other than the study procedure.
- **Yes:** The adverse event occurred as a result of protocol procedures, (eg, venipuncture)

7.2.2. Assessment of Severity

The severity grading of AEs will be assessed as Grade 1, 2, 3, or 4 using the GSI Grading Scale for Severity of Adverse Events and Laboratory Abnormalities ([Appendix 3](#)). For AEs associated with laboratory abnormalities, the event should be graded on the basis of the clinical severity in the context of the underlying conditions; this may or may not be in agreement with the grading of the laboratory abnormality.

7.3. Investigator Requirements and Instructions for Reporting Adverse Events and Serious Adverse Events to Gilead

Requirements for collection prior to study drugs initiation:

After informed consent, but prior to initiation of study drugs, the following types of events should be reported on the case report form (eCRF): all SAEs and adverse events related to protocol-mandated procedures.

Adverse Events

Following initiation of study drugs, collect all AEs, regardless of cause or relationship, until 30 days after last administration of study drugs and report to the eCRF database as instructed.

All AEs should be followed up until resolution or until the adverse event is stable, if possible. Gilead Sciences may request that certain AEs be followed beyond the protocol defined follow up period.

Serious Adverse Events

All SAEs, regardless of cause or relationship, that occur after the subject first consents to participate in the study (ie, signing the informed consent) and throughout the duration of the study, including the protocol-required post treatment follow-up period, must be reported to the eCRF database and Gilead Drug Safety and Public Health (DSPH) as instructed. This also includes any SAEs resulting from protocol-associated procedures performed after informed consent is signed.

Investigators are not obligated to actively seek SAEs after the protocol defined follow up period; however, if the investigator learns of any SAEs that occur after study participation has concluded and the event is deemed relevant to the use of study drugs, he/she should promptly document and report the event to Gilead DSPH.

Prior treatment history is collected as part of the study entry criteria and evaluation of individual patient characteristics and will not be generating lack of effect reports as this is outside the scope of the present clinical study. However, investigators should report any cases of lack of effect that they feel appropriate regarding the previous treatment regimen as spontaneous reports to the relevant authorities or marketing authorisation holders.

- All AEs and SAEs will be recorded in the eCRF database within the timelines outlined in the eCRF completion guideline.

Electronic Serious Adverse Event (eSAE) Reporting Process

- Site personnel record all SAE data in the eCRF database and from there transmit the SAE information to Gilead DSPH within 24 hours of the investigator's knowledge of the event. Detailed instructions can be found in the eCRF completion guidelines.
- If for any reason it is not possible to record the SAE information electronically, ie, the eCRF database is not functioning, record the SAE on the paper serious adverse event reporting form and submit within 24 hours to

Gilead DSPH: [contact]
 Email: [contact]

- As soon as it is possible to do so, any SAE reported via paper must be transcribed into the eCRF Database according to instructions in the eCRF completion guidelines.
- If an SAE has been reported via a paper form because the eCRF database has been locked, no further action is necessary.
- For fatal or life-threatening events, copies of hospital case reports, autopsy reports, and other documents are also to be submitted by e-mail or fax when requested and applicable. Transmission of such documents should occur without personal subject identification, maintaining the traceability of a document to the subject identifiers.
- Additional information may be requested to ensure the timely completion of accurate safety reports.
- Any medications necessary for treatment of the SAE must be recorded onto the concomitant medication section of the subject's eCRF and the event description section of the SAE form.

7.4. **Gilead Reporting Requirements**

Depending on relevant local legislation or regulations, including the applicable US FDA Code of Federal Regulations, the EU Clinical Trials Directive (2001/20/EC) and relevant updates, and other country-specific legislation or regulations, Gilead may be required to expedite to worldwide regulatory agencies reports of SAEs, serious adverse drug reactions (SADRs), or suspected unexpected serious adverse reactions (SUSARs). In accordance with the EU Clinical

Trials Directive (2001/20/EC), Gilead or a specified designee will notify worldwide regulatory agencies and the relevant IEC in concerned Member States of applicable SUSARs as outlined in current regulations.

Assessment of expectedness for SAEs will be determined by Gilead using reference safety information specified in the investigator's brochure or relevant local label as applicable.

All investigators will receive a safety letter notifying them of relevant SUSAR reports associated with any study drugs. The investigator should notify the IRB or IEC of SUSAR reports as soon as is practical, where this is required by local regulatory agencies, and in accordance with the local institutional policy.

7.5. **Toxicity Management**

7.5.1. **RBV Dose Adjustments**

Dose reduction or discontinuation of RBV due to toxicity should be performed according to the Japanese Rebetol® product label. Information is provided in [Table 7-1](#) and [Table 7-2](#).

In the event a female partner of a male subject becomes pregnant, the male subject must permanently discontinue RBV, however they can continue SOF/VEL FDC.

Table 7-1. RBV Dose Reduction Guidelines for Non-Cirrhotic Subjects

Test items	Value	Ribavirin
Neutrophil count	< 500 /mm ³	Discontinue
	< 50,000 /mm ³	Discontinue
	< 25,000/mm ³	Discontinue (resumption of dosing not allowed)
Platelet count	< 10 g/dL	Reduce dose 600 mg/day → 400 mg/day 800 mg/day → 600 mg/day 1,000 mg/day → 600 mg/day
	< 8.5 g/dL	Discontinue
Hemoglobin level (No cardiac disease or history of cardiac disease)	< 10 g/dL, or during administration, reduction of 2 g/dL or more relative to Day 1 persists for 4 weeks	Reduce dose 600 mg/day → 400 mg/day 800 mg/day → 600 mg/day 1,000 mg/day → 600 mg/day
	< 8.5 g/dL, or after dose reduction, less than 12 g/dL even after 4 weeks	Discontinue
Hemoglobin level (Cardiac disease or history of cardiac disease present)	< 10 g/dL, or during administration, reduction of 2 g/dL or more relative to Day 1 persists for 4 weeks	Reduce dose 600 mg/day → 400 mg/day 800 mg/day → 600 mg/day 1,000 mg/day → 600 mg/day
	< 8.5 g/dL, or after dose reduction, less than 12 g/dL even after 4 weeks	Discontinue

Source: Japan Rebetol® Product Label {[MSD K.K. Kudan-kita Chiyoda-ku 2016](#)}

Table 7-2. RBV Dose Reduction Guidelines for Cirrhotic Subjects

Test items	Value	Ribavirin
Neutrophil count	< 500 /mm ³	Discontinue
	< 50,000 /mm ³	Discontinue
Platelet count	< 25,000/ mm ³	Discontinue (resumption of dosing not allowed)
	< 11 g/dL at Week 1 to 4 after start of administration	Reduce dose 600 mg/day → 200 mg/day 800 mg/day → 400 mg/day 1,000 mg/day → 400 mg/day
	< 10 g/dL at Week 5 to 12 after start of administration	
Hemoglobin level (No cardiac disease or history of cardiac disease)	< 8.5 g/dL	Discontinue
	< 11 g/dL at Week 1 to 4 after start of administration or during administration, reduction of 2 g/dL or more relative to Day 1 persists for 4 weeks	Reduce dose 600 mg/day → 200 mg/day 800 mg/day → 400 mg/day 1,000 mg/day → 400 mg/day
	< 10 g/dL at Week 5 to 12 after start of administration or during administration, reduction of 2 g/dL or more relative to baseline persists for 4 weeks	
Hemoglobin level (Cardiac disease or history of cardiac disease present)	< 8.5 g/dL, or after dose reduction, less than 12 g/dL even after 4 weeks	Discontinue

Source: Japan Rebetol® Product Label {MSD K.K. Kudan-kita Chiyoda-ku 2016}

Once RBV has been withheld due to either a laboratory abnormality or clinical manifestation, an attempt may be made to restart RBV at a lower daily dose with subsequent step-wise increase in the daily dose as clinically indicated. However, it is not recommended that the RBV daily dose be increased to the original assigned dose.

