3.2. Study Treatments

Approximately 110 subjects will be randomized in a 1:1 ratio to one of the following two groups:

- SOF/VEL FDC tablet (400/100 mg) plus RBV for 12 weeks
- SOF/VEL FDC tablet (400/100 mg) plus RBV for 24 weeks

Randomization will be stratified by cirrhosis status (presence/absence) and HCV genotype (genotype 1/genotype 2). Approximately 20 subjects will have Child-Pugh-A compensated cirrhosis.

The number of subjects by HCV genotype to be enrolled in the study is presented below:

HCV Genotype	Number of Subjects Enrolled
1	approximately 90
2	approximately 20
Total	approximately 110

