 - f) Creatinine clearance (Cr_{cl}) < 50 mL/min as calculated by the Cockcroft-Gault equation
{[Cockcroft et al 1976](#)}
 - g) Hemoglobin < 10 g/dL
 - h) Albumin < 3 g/dL
 - i) International Normalized Ratio of prothrombin time (INR) > 1.5 × ULN unless subject has known hemophilia or is stable on an anticoagulant regimen affecting INR
 - j) Neutrophil count < 500/µL
- 8) Donation or loss of more than 400 mL blood within 2 months prior to Day 1
- 9) Use of any prohibited concomitant medications as described in Section [5.6](#)
- 10) Known hypersensitivity to sofosbuvir, velpatasvir, or ribavirin or the metabolites or formulation excipients
- 11) Known contraindication to sofosbuvir and/or ribavirin

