5.3.4. Dosage and Administration of Ribavirin (RBV)

RBV will be administered in accordance with approved RBV labeling in Japan, see [Table 5-1](#) below.

Table 5-1. Dosing and Administration of RBV in Japan

Body weight at Day 1	Ribavirin dosage		
	Daily dosage	After morning meal	After evening meal
≤ 60 kg	600 mg	200 mg	400 mg
> 60 kg to ≤ 80 kg	800 mg	400 mg	400 mg
> 80 kg	1,000 mg	400 mg	600 mg

Source: Japan Rebetol® Product Label {[MSD K.K. Kudan-kita Chiyoda-ku 2016](#)}

RBV dose modification or discontinuation should be performed in accordance with the RBV package insert (refer to Section [7.5.1](#)).

RBV should be dosed with food and SOF/VEL FDC when appropriate.

RBV capsule (200 mg) will be supplied by Gilead Sciences for all applicable subjects.

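### Table 7-2 gives no absolute hemoglobin trigger for reducing ribavirin in cirrhotic subjects after Week 12, although one arm takes ribavirin to Week 24

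*Protocol*

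**What the plan says.** Protocol Section 3.2 randomizes subjects 1:1 to 12 or 24 weeks. The longer regimen is "SOF/VEL FDC tablet (400/100 mg) plus RBV for 24 weeks". Randomization is stratified by cirrhosis, and "Approximately 20 subjects will have Child-Pugh-A compensated cirrhosis".

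Section 7.5.1 sets the source of the ribavirin rules: "Dose reduction or discontinuation of RBV due to toxicity should be performed according to the Japanese Rebetol® product label". Section 5.3.4 says the same ("RBV dose modification or discontinuation should be performed in accordance with the RBV package insert") and refers the reader to Section 7.5.1, where Tables 7-1 and 7-2 stand. The synopsis also ties ribavirin dose changes to the approved labeling.

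Table 7-2, for cirrhotic subjects, reduces ribavirin below 11 g/dL in Weeks 1 to 4 and then "< 10 g/dL at Week 5 to 12 after start of administration". That second entry appears in both hemoglobin blocks, with and without cardiac disease, and neither block has an entry for later weeks. The cardiac block adds a relative trigger, "reduction of 2 g/dL or more relative to baseline persists for 4 weeks". Discontinuation below 8.5 g/dL has no week limit.

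Table 7-1, "RBV Dose Reduction Guidelines for Non-Cirrhotic Subjects", reduces below 10 g/dL with no week limit.

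**The concern.** The week ranges in Table 7-2 fit a 12-week course, but cirrhotic subjects are also assigned to 24 weeks. Table 7-2 is otherwise the more cautious table: it has the early 11 g/dL trigger and larger dose steps (600 to 200 mg/day, against 600 to 400 mg/day in Table 7-1). Past Week 12 the order reverses, and at the same hemoglobin the table prompts a reduction without cirrhosis but not with it.

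The uncovered range matters on the protocol's own scale. For HIV-negative adults, Appendix 3 grades 9.0 to < 10.0 g/dL as Grade 2 and 7.0 to < 9.0 g/dL as Grade 3. SAP Section 7.2.1 counts subjects below 10 and below 8.5 g/dL at any post-baseline visit, with no Week 12 cut-off. Scheduled hematology after Week 12 is four-weekly, so a reduction that is not made at one visit may wait until the next.

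**Working it through.** The plan states no figure to reproduce. The check sets the table entries against the treatment schedule and then counts who could be exposed.

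**Weeks covered (Table 7-2, Section 3.2).** Weeks 1–4 plus Weeks 5–12 make 12 weeks. Uncovered in the long arm: 24 − 12 = 12 weeks, and 12/24 = 50% of dosing.

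**Visits covered (Section 6.3).** Hematology visits in the long arm at which the dose can still change are Weeks 1, 2, 3, 4, 5, 6, 8, 10 and 12 (9 visits) and Weeks 16 and 20 (2 visits). Week 24 is the end of treatment. Uncovered: 2/11 = 18%.

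**One value, 9 g/dL on an unreduced dose, read against the tables:**

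| Subject | Week 10 | Week 16 |
|---|---|---|
| Non-cirrhotic, no cardiac disease | Reduce | Reduce |
| Cirrhotic, no cardiac disease | Reduce | No printed action (9 is not below 8.5) |
| Cirrhotic, cardiac disease | Reduce | Reduce only if a fall of at least 2 g/dL has lasted 4 weeks |

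In the last row, a subject who started at 10.5 g/dL has fallen by 10.5 − 9 = 1.5 g/dL and does not meet the relative trigger.

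The row labels of both tables are displaced in the text available for this review. The blocks carrying the relative trigger were read as the cardiac ones. The missing weeks do not depend on that reading, because the Week 5 to 12 limit is in both blocks.

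**Ceiling on exposure.** About 20 cirrhotic subjects × 1/2 = about 10 in the 24-week arm. Over two visits that is 10 × 2 = 20 subject-visits, which is opportunity and not expected events. The cardiac share is not given. If it were 0%, 20% or 40% (an assumption), 10, 8 or 6 subjects would have no printed reduction threshold after Week 12 (20, 16 or 12 subject-visits); the rest would lack only the absolute one.

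**Who within the ceiling could benefit.**
- Screening excludes "Hemoglobin < 10 g/dL".
- A cirrhotic subject below 11 g/dL in Weeks 1–4 or below 10 g/dL in Weeks 5–12 has already met a trigger.
- The printed steps start only from 600, 800 or 1,000 mg/day and end at 200 or 400 mg/day. A subject already reduced has no second printed step in any week.

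That leaves mainly subjects still on an unreduced dose whose hemoglobin first falls to 8.5 to < 10 g/dL after Week 12.

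**The case against.** The strongest objection is that the label is the rule and the tables are information drawn from it. If the label prints the same weeks, the protocol copied its source faithfully. If the label covers later weeks, that rule already binds. This stands in part: a reader might infer that the label has a gap, or that subjects would be left without a rule, and the documents support neither because the label is not among them. It does not remove the inconsistency between the two printed tables, which are where Section 5.3.4 sends the reader.

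A second objection is that investigators can act without a printed trigger. This also stands. Nothing forbids an earlier reduction, and safety reviews (Section 1.5), unscheduled visits (Section 6.6) and central monitoring of safety data (Section 9.1.6) remain. The paragraph below Table 7-2 lets ribavirin withheld for a laboratory abnormality be restarted at a lower dose, so it would be too strong to say that nothing lies between full dose and stopping. But that paragraph sets no threshold, and Section 3.4 deals with stopping and not with reducing.

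A reader might also want an expected count from the earlier 24-week study in Section 1.2.3.3.4, where 5 of 41 subjects (12.2%) had ribavirin modified or interrupted for adverse events. That figure covers any event over a whole course in another study population and says nothing about first anemia after Week 12, so it is not used here.

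**Conclusion.** The point holds for the printed table. After Week 12, Table 7-2 has no absolute hemoglobin trigger for reducing ribavirin. Cirrhotic subjects without cardiac disease have no printed reduction threshold at all, and those with cardiac disease keep only the relative one. Table 7-1 continues to apply 10 g/dL.

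The size is small: at most about 10 subjects at two scheduled visits, if enrollment and allocation go as planned. The number a correction would help is unknown and probably small. A reader might take the 50% of dosing weeks as a measure of harm, or suppose that the efficacy or safety analyses are affected. The documents support neither. This is a low-severity patient-safety point that the sponsor could correct.

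**What to change.** 1. Check the Japanese Rebetol label. If it gives a rule for cirrhotic patients after Week 12, print that rule in Table 7-2.
2. If it does not, replace the Week 5 to 12 range with *Week 5 to end of treatment* at < 10 g/dL in both hemoglobin blocks, and keep the printed dose steps.
3. In the second case, state under the table and in Section 7.5.1 that the trigger after Week 12 is a protocol rule added to the label. The table's source line, the synopsis and Section 5.3.4 may need matching wording, because they tie dose changes to the label.

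The cost is a small protocol amendment, with IRB/IEC approval before implementation (Sections 9.1.2 and 9.2.1) at about 20 centers, and a notice to sites. It can travel with another amendment. There may be slightly more ribavirin reductions in the 24-week arm. No visits or tests are added, because hematology is already drawn at Weeks 16 and 20.
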